6.5. Immunogenicity Endpoints

Blood samples for immunogenicity (ADA and NAb) will be collected at the time points described in the Schedule of Activities given in the protocol. Samples will be tested for ADA first, only confirmed ADA positive samples and the corresponding baseline samples will be tested in the NAb assay.

Incidence of the development of anti-drug antibodies (ADAs)/neutralizing antibodies (NAbs) will be summarized by descriptive statistics presented separately for SAD and MAD. The treatment dose will be characterized by the total dose and routes of exposure (SC and IV).

7. HANDLING OF MISSING VALUES

For the analysis of safety endpoints, the sponsor data standard rules for imputation will be applied. Longitudinal modeling will use available data only, no imputation will be done.

7.1. Concentrations Below the Limit of Quantification

In all PK data presentations (except listings), concentrations below the limit of quantification (BLQ) will be set to zero. (In listings BLQ values will be reported as "<LLQ", where LLQ will be replaced with the value for the lower limit of quantification).

In all biomarker data presentations (except listings), biomarker values below the limit of quantification (BLQ) will be set to LLQ/2. (In listings BLQ values will be reported as "<LLQ", where LLQ will be replaced with the value for the lower limit of quantification).

7.2. Deviations, Missing Concentrations and Anomalous Values

In summary tables and plots of median profiles, statistics will be calculated having set concentrations to missing if 1 of the following cases is true:

- 1. A concentration has been collected as ND (ie not done) or NS (ie no sample),
- 2. A deviation in sampling time is of sufficient concern or a concentration has been flagged anomalous by the pharmacokineticist.

Note that summary statistics will not be presented at a particular time point if more than 50% of the data are missing.

7.3. Pharmacokinetic Parameters

Actual PK sampling times will be used in the derivation of PK parameters.

If a PK parameter cannot be derived from a subject's concentration data, the parameter will be coded as NC (ie, not calculated). (Note that NC values will not be generated beyond the day that a subject discontinues.)

In summary tables, statistics will be calculated by setting NC values to missing; and statistics will be presented for a particular dose with ≥ 3 evaluable measurements.

If an individual subject has a known biased estimate of a PK parameter (due for example to an unexpected event such as vomiting before all the compound is adequately absorbed in the body), this will be footnoted in summary tables and will not be included in the calculation of summary statistics or statistical analyses.

8. STATISTICAL METHODOLOGY AND STATISTICAL ANALYSES

8.1. Statistical Methods

As this is an exploratory study, no formal hypothesis testing will be performed. CCI

Statistical Analyses

All efficacy data from parts 1, 2 and 3will be listed and summarized separately. Safety data will also be summarized combining all three parts as well as separately. Percentages will be presented to one decimal place in all summaries. Minimum and maximum values will be presented to the same number of decimal places as collected on the CRF or with the laboratory screening panel; mean and median will be presented to one further decimal place; standard deviations will be presented to two further places.

In data presentations, results will be sorted by increasing dose level and by study part (SAD/MAD, Nasal Polyps, or Atopic Dermatitis) as appropriate.

Binary variables will be summarized by the number of responders and the number of subjects with data. Percentages will be presented for both observed cases (number of subjects with data at the time point for the denominator) and by non-response imputation (NRI) (number of subjects with data at baseline in the denominator).

Pharmacokinetic Analysis

To assess the pharmacokinetics of PF-06817024, the PK parameters detailed in Section 6.3 will be listed and summarized for subjects in the PK analysis set (as defined in Section 5.2.2). Missing values will be handled as detailed in Section 7. Each PK parameter will be summarized by cohort and will include the set of summary statistics as specified in the table below:

Type of Dosing	Parameter	Summary Statistics
Single Dose [†]	AUC _{last} , AUCinf, AUCinf (dn), C _{max} ,	N, arithmetic mean, median, cv%,
	Cmax(dn), CL, Vss, CL/F, Vz/F	standard deviation, minimum,
		maximum, geometric mean and
		geometric cv%.
	T _{max}	N, median, minimum, maximum.
	t _{1/2}	N, arithmetic mean, median, cv%,
		standard deviation, minimum,
		maximum.
Multiple Dose‡	AUC _{tau} , AUCtau (dn), C _{av} , C _{max} ,	N, arithmetic mean, median, cv%,
	C _{max} (dn), Cmin, Rac AUCtau, Rac	standard deviation, minimum,
	C _{max}	maximum, geometric mean and
		geometric cv%.
	T _{max}	N, median, minimum, maximum.
	t _{1/2}	N, arithmetic mean, median, cv%,
		standard deviation, minimum,
		maximum.

Table 2. PK Parameters to be Summarized Des	scriptively
---	-------------

 \dagger = single dose subjects in Part 1 and all subjects in Part 2, \ddagger = multiple dose subjects in Part 1 and all subjects in Part 3.

There will be 1 summary table for each Part presenting all PK parameters. Each table will include data from all cohorts in the Part and will be paged by cohort. The treatment subheading will include the cohort number and dose information.

To assess the relationship between the PK parameters and dose, dose normalized AUC_{inf} and C_{max} will be plotted against dose (using a logarithmic scale), and will include individual subject values and the geometric means for each dose from Part 1 only. Geometric means will have a different symbol than the individual values. The values will be dose normalized (to a 1mg dose) by dividing the individual values and raw geometric means by dose. A footnote will be added to the plots to indicate that geometric means are presented and that data from both cohorts are presented on the plot.

Supporting data from the estimation of $t_{\frac{1}{2}}$ and AUC_{inf} will be listed by analyte where applicable: terminal phase rate constant (k_{el}); goodness of fit statistic from the log-linear regression (r²); the percent of AUC_{inf} based on extrapolation (AUC_{extrap%}); and the first, last, and number of time points used in the estimation of k_{el}. This data may be included in the clinical study report.

Presentations for PF-06817024 concentrations will include:

- A listing of all concentrations sorted by subject ID, cohort, dose and nominal time post first dose. The concentration listing will also include the actual times. Deviations from the nominal time will be given in a separate listing.
- A summary of concentrations by cohort, dose and nominal time post first dose, where the set of statistics will include n, mean, median, standard deviation, coefficient of variation (cv), minimum, maximum and the number of concentrations above the lower limit of quantification.
- Median concentrations time plots (on both linear and semi-log scales) against nominal time post first dose by cohort and dose (all cohorts on the same plot per scale, based on the summary of concentrations by cohort, dose and time post-dose).
- Mean concentrations time plots (on both linear and semi-log scales) against nominal time post first dose by cohort and dose (all cohorts on the same plot per scale, based on the summary of concentrations by cohort, dose and time post-dose).
- Individual concentration time plots by cohort and dose (on both linear and semi-log scales) against actual time post first dose (there will be separate spaghetti plots for each cohort per scale).
- Individual concentration time plots by subject (on both linear and semi-log scales) against actual time post first dose (there will be separate plots for each subject).

The length of time used for the x-axes of these plots will be decided on review of the data, and will depend on how long the PF-06817024 concentration is quantifiable in the matrix.

For summary statistics, median and mean plots by sampling time, the nominal PK sampling time will be used, for individual subject plots by time, the actual PK sampling time will be used.

NOTE: Cohort 3 in Part 1 had subjects receiving both single and multiple doses. Therefore all listings, PK parameter summaries, concentration-time profile plots and any other PK data summarizations or analyses should separate single and multiple dose subjects from Cohort 3 treating them as two distinct sub-groups.

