As this study is currently ongoing and blinded, only summary, preliminary, blinded, unaudited safety, tolerability, PK, and immunogenicity data are available and presented below. Given the limited number of AD subjects recruited, the cumulative safety data to date primarily reflect the safety and tolerability in healthy subjects and subjects with CRSwNP (Parts 1 and 2). As of the above cutoff data, adverse effects (AEs) have been observed in 57 of 71 subjects (80.3%) receiving blinded therapy. The most commonly reported treatment-emergent adverse events (TEAEs) have fallen under the Medical Dictionary for Regulatory Activities (MedDRA) System Organ Classes (SOC) of Infections and Infestations (36.6%), Gastrointestinal Disorders (19.7%), Injury, Poisoning and Procedural Complications (16.9%), Musculoskeletal and Connective Tissue Disorders (15.5%), and Nervous System Disorders (15.5%). The most common (occurring in 3 or more subjects) AEs by Preferred Term were: upper respiratory tract infection (10 subjects, 14.1%); sinusitis, pain in extremity, nasal congestion, ecchymosis (5 subjects, 7.0%, each); and oral herpes, nausea, back pain, and dizziness (3 subjects, 4.2%, each). The safety profile has been generally similar across the healthy and CRSwNP subjects. Adverse effects in the System Organ Class of Respiratory, Thoracic, and Mediastinal Disorders appeared to be more frequent in the subjects with CRSwNP than in healthy subjects, likely reflective of their underlying disease. A variety of mild transfusion-related reactions were noted in the early cohorts of Part 1 of Study C0341001 in healthy subjects, but these were mitigated when the infusion time was increased from 60 to 90 minutes. In general, ongoing review of the preliminary data has revealed the AEs to be generally mild-moderate in severity and self-limited.

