Subjects in the multiple dose cohorts (Cohorts 3 through 5 and Cohort 7) will be confined to the clinic from the day prior to dosing and through completion of Day 5 evaluations (minimum of 96 hours post first dose administration), and 48 hours after the second dose administration. Subjects will return for outpatient follow-up visits per the Schedule of Activities (SoA) Table C.

Throughout the study, adverse events (AEs) will be solicited, with specific attention to infusion and injection site reactions (ISR) and those linked to immune reactions. ADA responses will be monitored from samples collected at baseline and at the additional times post-dose as specified in the SoA. Samples found to be positive in the ADA assay will be further evaluated for neutralizing antibody (NAb) activity. Subjects having an unresolved adverse event that is possibly related to an ADA immune response will be asked to return for extended follow-up visit(s) at up to 3 month intervals beyond the last follow-up visit for up to 12 months after last drug administration or until the adverse event or its sequelae resolve or stabilize at a level acceptable to the investigator and Sponsor concurs with the investigator's assessment (see SoA). Subjects in any cohort may be confined beyond the period defined in the schedule of activities at the discretion of the investigator to accommodate the frequency of required follow-up. Subjects who are withdrawn from study for reasons other than safety may be replaced at the discretion of the sponsor.

If operational logistics or safety analysis prohibits any of the pre-specified cohorts from receiving their second dose (eg, required safety or PK data are not available in time for the second dose) as planned for Cohorts 3-5 or Cohort 7, or the Sponsor determines not to proceed with all multiple dose cohorts based upon the review of emerging data, the affected cohort(s) will return for outpatient follow-up visits per the SoA Table B. Additional subjects may be randomized into the following cohorts (Cohorts 10-12) as needed to complete the multiple dose portion of the study. The additional multiple dose cohorts would not be randomized until the dosing criteria for multiple dose cohorts (see Section 3.3) were completed:

- Cohort 10 (n=8): 100 mg active (n=6) or placebo (n=2), IV x 2 doses.
- Cohort 11 (n=8): 300 mg active (n=6) or placebo (n=2), IV x 2 doses.
- Cohort 12 (n=8): 1000 mg active (n=6) or placebo (n=2), IV x 2 doses.

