5.4.3. Administration

PF-06817024 and placebo are administered intravenously and subcutaneously.

Following an overnight fast of least 10 hours (except for Part 3 as specified in the IP Manual), subjects will receive study treatment at approximately 08:00 hours (plus or minus 4 hours). Study treatment will be administered as approximately 60-90 minute intravenous infusion (Parts 1 and 2), approximately 90 minute intravenous infusion for Part 3, as specified in the IP manual, using a calibrated infusion pump for subjects receiving IV administration (this may be modified up to 120 minutes by the Sponsor study team and the PI). Study drug must not be administered as an IV push or bolus. The start and stop time of the infusion will be recorded. Time 0 is the time when the study drug infusion begins. The infusion rate and amount of volume infused will be recorded. For SC administration, study treatment will be injected subcutaneously. Each injection should occur at a different site on the abdomen or thigh, approximately 1 cm apart. Administer study treatment according to the IP Manual.

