8.1.6. Adverse Events

Data will be presented by study part (SAD/MAD, Nasal Polyps and Atopic Dermatitis) and cumulatively across all study parts. Adverse events will be reported in accordance with the sponsor reporting standards.

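### Infusion time rose from 60 to 90 minutes during Part 1, but the visible SAP never uses duration, so dose-ordered displays of infusion-related reactions can mix dose with duration

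*SAP*

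**What the plan says.** - **The change.** Protocol 1.2.5.1 reports that a variety of mild "reactions were noted in the early cohorts of Part 1 of Study C0341001 in healthy subjects", and that "these were mitigated when the infusion time was increased from 60 to 90 minutes". It does not name the cohort or dose at which the change was made.
- **Infusion time.** Protocol 5.4.3: "Study treatment will be administered as approximately 60-90 minute intravenous infusion (Parts 1 and 2"), and "approximately 90 minute intravenous infusion for Part 3". No duration is tied to a cohort. The same section says "The start and stop time of the infusion will be recorded".
- **Order of enrolment.** Protocol 3.1.1 enrols Cohorts 1 to 6 one after another from the lowest dose upward. It also solicits adverse events (AEs) "with specific attention to infusion and injection site reactions (ISR) and those linked to immune reactions".
- **Display.** SAP 8.1: "In data presentations, results will be sorted by increasing dose level and by study part", qualified by a closing remark that this applies where appropriate. Safety data are to be shown for each part and for all three parts combined. SAP 8.1.6: "Adverse events will be reported in accordance with the sponsor reporting standards". SAP 8.1.10 plans no other safety displays.

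**The concern.** Safety and tolerability is the Part 1 primary objective (Protocol 2.1.1), and infusion reactions are singled out for attention. The protocol itself says that a change in delivery during Part 1 reduced them. With sequential escalation, a change in calendar time is also a change along the dose axis. A reader of a dose-ordered AE table would see reactions by dose with no sign that infusion time also changed.

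Two misreadings are possible. Reactions may appear to fall as dose rises when the longer infusion is the cause, or a true increase with dose may be offset and go unseen. The cumulative table adds to this by combining the subcutaneous cohort, the 60 to 90 minute infusions of Parts 1 and 2, and the roughly 90 minute infusions of Part 3.

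**Working it through.** No sample size, power or test is involved. The check is whether the documents support a link between dose and duration, and how firmly.

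**1. Reproduce the protocol's figure.** The healthy single-dose IV medians for Tmax in Protocol Table 1 are 3.00, 1.76, 2.00, 2.00 and 1.78 h. Their range is 1.76 to 3.00 h, which matches Protocol 1.2.5.2.

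**2. Minimum Tmax as an indirect marker.** For IV cohorts the nominal 1-hour PK sample follows the end of infusion (Schedule of Activities Table A, footnote a; Table D, footnote b for Part 2). If that rule was kept, a subject's Tmax is an upper limit on that subject's infusion time. Minutes = hours × 60.

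| IV cohort | N | Median (h) | Range (h) | Minimum (min) |
|---|---|---|---|---|
| 10 mg healthy | 6 | 3.00 | 1.15–4.05 | 69 |
| 30 mg healthy | 6 | 1.76 | 1.02–2.33 | 61 |
| 100 mg healthy | 7 | 2.00 | 1.03–8.03 | 62 |
| 300 mg healthy | 6 | 2.00 | 1.53–8.00 | 92 |
| 1000 mg healthy | 6 | 1.78 | 1.53–4.00 | 92 |
| 300 mg CRSwNP | 11 | 2.00 | 1.00–170 | 60 |

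The healthy cohorts step from about 60–70 to about 92 minutes, which fits a move from 60 to 90 minute infusions. Each minimum is one subject, though. A minimum of 92 minutes does not prove a 90 minute infusion, because a late peak after a shorter infusion would look the same.

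**3. Evidence against a clean break.**
- *30 mg.* With N = 6, the third and fourth ordered values sum to 2 × 1.76 = 3.52. The fourth is at most 2.33, so the third is at least 3.52 − 2.33 = 1.19 h and at most 1.76 h. At least one 30 mg subject therefore peaked between about 71 and 106 minutes, which fits a longer infusion or a late sample below 100 mg.
- *CRSwNP at 300 mg.* The minimum is 1.00 h. Either some 300 mg infusions lasted about an hour, or the marker is unreliable.
- *Second 100 mg dose.* The median Tmax is 1.54 h in 4 subjects (Protocol 1.2.5.2). Protocol Table 3 places this dose after Cohort 4's first dose, so a 90 minute infusion by then is plausible. A median of four is the mean of the middle two, however, and (1.05 + 2.03)/2 = 1.54 would give the same figure.

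**4. Duration, not mg per minute.** Suppose 60 minutes up to 100 mg and 90 minutes above. Then 10/60 = 0.17, 30/60 = 0.50, 100/60 = 1.67, 300/90 = 3.33 and 1000/90 = 11.1 mg/min. Delivery in mg/min still rises at every step.

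**5. Numbers involved.** At 10, 30 and 100 mg IV the plan has 3 × 6 = 18 active and 3 × 2 = 6 placebo subjects (Table 1 counts 6 + 6 + 7 = 19 active). At 300 and 1000 mg it has 2 × 6 = 12 active and 2 × 2 = 4 placebo. One reaction is 1/6 = 16.7 points in a cohort's active arm and 1/2 = 50 points in its placebo arm.

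**The case against.** The strongest reply has four parts.

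- **Scope.** The quoted SAP sentence only sets a sort order. No hypothesis is tested (SAP 4.1) and no dose-response model appears in the visible text. The reactions were mild. This stands: the point is about reading a descriptive table of one class of event.
- **Unseen text.** AE reporting is left to sponsor standards, and parts of the SAP are redacted. A display by duration may exist there. This also stands; if so, the sponsor need only cite it. SAP 6.2.5 would list additional safety data held in the database, but a listing does not warn a reader of the tables.
- **Limited remedy.** If dose and duration coincide completely on first doses, a table by duration relabels the same groups. The Cohort 3 second dose does not rescue this, since it is tied to repeat exposure in 4 subjects. This stands as a limit, but disclosure is still worth having.
- **Inference from Table 1.** A reader might infer that the change fell exactly between 100 and 300 mg. The documents do not say so, and step 3 shows evidence against a clean break. The concern does not need that location; it needs only a change during Part 1 and sequential escalation.

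Three other strong readings are not supported. Infusion rate does not run against dose order (step 4). The wider primary safety data (other AEs, laboratory tests, vital signs, ECG) are not shown to be affected. Nor can a false trend be quantified, as no reaction rates are given. SAP 8.1.6 also does not say how placebo is grouped for AEs, so a mixed-duration placebo is a possibility, not a stated plan.

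**Conclusion.** The point holds in limited form. The protocol states the change in infusion time and its link to reactions, and Part 1 enrolled in rising dose order, so shorter infusions tend to go with lower doses. Table 1 is consistent with this. The visible SAP orders results by dose, combines parts and does not use duration, so the display of infusion-related reactions can mix the two.

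The direction and size of any distortion cannot be calculated. What can be said is that each cohort's percentage turns on very few subjects. The conclusion assumes that the change was made once in calendar time, with few exceptions. Replacement subjects dosed later in Cohorts 1 to 4 would blur the link and give some overlap. It also assumes that the unseen sponsor standards contain no breakdown by duration.

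**What to change.** In SAP 8.1.6:

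1. Tabulate actual infusion duration by cohort and dose occasion, from the recorded start and stop times.
2. Define infusion-related reactions in advance (for example, AEs starting on the infusion day plus reported infusion-site reactions). Summarise them by actual duration class for active and placebo, comparing active with placebo of the same class, and show Cohort 3 first and second doses separately. Fix the class boundary before reactions are tabulated; the midpoint (60 + 90)/2 = 75 minutes is one choice. Flag interrupted or stopped infusions, because under Protocol 5.5 a reaction can itself lengthen or cut short an infusion.
3. Footnote the dose-ordered and cumulative AE tables: for these reactions, dose and infusion duration may not be separable.

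The cost is one derived variable, two small tables and a footnote, using data already collected. No treatment rule changes. The drawback is small cells (about 6 and 4 planned placebo subjects if the split in step 5 applies). If dose and duration coincide completely, the tables disclose the confounding but cannot remove it.

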1.2.5.2. PK Data

Based on a preliminary, draft dataset obtained in January 2018 and including interim data from subjects in the first two parts of the study, a non-compartmental PK analysis was performed and the derived PF-06817024 PK parameters are summarized descriptively in Table 1.

Following single IV doses in healthy subjects, the median time for occurrence of maximal concentration (T_{max}) ranged between 1.76 and 3 hours, while the median T_{max} after SC administration (30 mg) was 338 hours (\approx 14 days). PF-06817024 had a prolonged half-life ($t_{1/2}$) with mean values ranging from 79 to 94 days across all single dose healthy volunteer cohorts. Both maximal plasma concentration (C_{max}) and area under the concentration-time curve from time 0 to infinity (AUC $_{inf}$) appeared to be approximately dose proportional in healthy subjects across the 10-1000 mg IV range (see Table 1), indicating that PF-06817024 exhibits linear kinetics in humans within this dose range. Clearance (CL) values (geometric mean) ranged from 0.00206 L/h to 0.00259 L/h across all single IV dose healthy volunteer cohorts. Using the calculated geometric means of AUC $_{inf}$ after single IV infusion and SC administration of the same dose (30 mg) in healthy subjects (8579/14590, see Table 1), the bioavailability (F) after SC administration is approximately 59% relative to IV infusion.

Multiple dose PK data were available only for 4 healthy subjects from the 100 mg IV cohort who received an additional 100 mg IV dose. The (geometric) mean C_{max} after the second dose was 42.47 µg/mL (geometric CV of 11%) across these 4 subjects and the associated median T_{max} was 1.54 hours. The (geometric) mean area under the concentration-time curve from the time of the second dose until 720 hours post-dose (AUC_{τ}) and until infinity (AUC_{inf}) was 16540 (geometric CV of 13%) and 73400 µg•hr/mL (geometric CV of 23%) respectively. Finally, the mean calculated $t_{1/2}$ after the second dose was 108 days (standard deviation (SD) of 10).

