Figure 1 demonstrates the study design with the select SAD cohorts rolling over into the multiple dose component. Depending on the safety, ^{CCI} and pharmacokinetic data available, dose escalation may be adjusted to doses other than those planned in the study. Intermediate doses can be evaluated instead of or in addition to the planned dose levels. A possible dosing scenario is included in the schematic.

• Cohort 1 (n=8): 10 mg active (n=6) or placebo (n=2), IV.

- Cohort 2 (n=8): 30 mg active (n=6) or placebo (n=2), IV.
- Cohort 3 (n=8): 100 mg active (n=6) or placebo (n=2), IV x 2 doses. [n=4 in MAD cohort].
- Cohort 4 (n=8): 300 mg active (n=6) or placebo (n=2), IV x 2 doses. [no MAD].
- Cohort 5 (n=8): 1000 mg active (n=6) or placebo (n=2), IV x 2 doses. [no MAD].
- *Cohort 6 (n=8): 2000 mg active (n=6) or placebo (n=2), IV.* [dose escalation stopped before 2000 mg dose group].
- Cohort 7 (n=8): 100 mg (first dose) followed by 300 mg (second dose) active (n=6) or placebo (n=2), SC. [Second dose not given, 100 mg dose changed to 30 mg].

2.2. Part 2:

One or more cohorts of CRSwNP patients will receive a single dose of PF-06817024. Randomization will occur after safety data from Day 8 and PK data through at least Day 5 of the same or higher dose in Part 1 of the study has been reviewed and deemed safe.

• Cohorts 8 and 9: Subjects in each cohort will be randomized in either a 1:1 or 2:1 (PF-06817024: placebo) ratio, depending on the number of cohorts and the emerging data. Up to approximately 10 active (per dose) and approximately 15 placebo (overall) subjects will be enrolled in Part 2 for a planned total of up to approximately 35 subjects.

2.3. Part 3

- Part 3 will consist of a single cohort of subjects with moderate to severe AD
- Cohort 13: Approximately 20 subjects in this cohort will be randomized to receive PF-06817024 or placebo in a 3:1 ratio (PF-06817024: placebo). Additional subjects up to a total of approximately 32 [28 actually enrolled] may be enrolled in a 3: 1 ratio (PF-06817024: placebo) CCI Subjects in this cohort randomized to PF-06817024 will receive a planned dosing regimen consisting of a 600 mg IV loading dose followed by 3 doses of 300 mg IV every 4 weeks.

Note that subjects were randomized 2:1 by site under protocol amendment 4 and then randomized centrally in a 3:1 ratio under amendment 5.

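### Do the Part 1 dose-normalised AUCinf and Cmax plots pool 30 mg IV with 30 mg SC?

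*SAP*

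**What the plan says.** The Pharmacokinetic Analysis part of SAP section 8.1 plots dose-normalised AUCinf and Cmax against dose on a logarithmic scale, for Part 1 only. The plot "will include individual subject values and the geometric means for each dose". Normalisation is done "by dividing the individual values and raw geometric means by dose". A footnote is to say that geometric means are shown and that "data from both cohorts are presented on the plot"; it does not name the cohorts.

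SAP section 2.1 lists "Cohort 2 (n=8): 30 mg active (n=6) or placebo (n=2), IV". For Cohort 7, the SC cohort, it notes "Second dose not given, 100 mg dose changed to 30 mg". Two Part 1 groups therefore received a single 30 mg dose, one by each route.

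For the tables, the same part of section 8.1 says "Each PK parameter will be summarized by cohort". A closing note requires that "any other PK data summarizations or analyses should separate single and multiple dose subjects from Cohort 3 treating them as two distinct sub-groups". Protocol section 9.3 describes a similar plot, with AUCtau in place of AUCinf, and also gives no route term.

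**The concern.** This is the only visible analysis whose stated aim is to relate PK parameters to dose. If a programmer grouped strictly by milligrams, the six IV and six SC subjects at 30 mg would share one geometric mean. Protocol section 1.2.5.2 reports that "the bioavailability (F) after SC administration is approximately 59% relative to IV infusion", and the Cmax gap between routes is wider still. The 30 mg point would then fall because of route, yet a reader could take the fall as departure from dose proportionality. The footnote does not settle the matter, since more than two cohorts contribute. The SAP does write a separation rule for Cohort 3 but none for the two routes at 30 mg.

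**Working it through.** **Inputs.** Protocol Table 1 (preliminary data), geometric mean (geometric CV), 6 subjects per route at 30 mg for both parameters:

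| | 30 mg IV | 30 mg SC |
|---|---|---|
| AUCinf (µg·hr/mL) | 14590 (28%) | 8579 (37%) |
| Cmax (µg/mL) | 12.26 (20%) | 2.471 (43%) |

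**Reproducing the protocol's own figure.** F = 8579/14590 = 0.588, which matches the stated 59%. The corresponding Cmax ratio is 2.471/12.26 = 0.20.

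**What pooling would give.** With equal numbers, the pooled geometric mean is the square root of the product, divided by 30 mg.

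- Cmax: √(12.26 × 2.471)/30 = 5.504/30 = 0.183. Against 30 mg IV (12.26/30 = 0.409) the ratio is 0.449, or 55% lower. Against the lowest IV mean (0.2395 at 10 mg) it is 0.766, or 23% lower.
- AUCinf: √(14590 × 8579)/30 = 11188/30 = 372.9. Against 30 mg IV (486.3) the ratio is 0.767, or 23% lower. Against the lowest IV mean (386.7 at 300 mg) it is 0.964, or 3.6% lower.

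A pooled Cmax mean would thus describe neither route. A pooled AUCinf mean would sit just under the IV series.

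**What separate means give.** The IV series for 10, 30, 100, 300 and 1000 mg runs 0.240, 0.409, 0.354, 0.325, 0.313 for Cmax and 438, 486, 445, 387, 421 for AUCinf. The SC cohort stands apart at 0.082 and 286.

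**Which of these the SAP leads to.**

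1. The normalisation sentence divides raw geometric means by dose, which most naturally refers to means already calculated. The visible SAP defines geometric means of AUCinf and Cmax in one place, SAP Table 2, and there the grouping is by cohort. That yields two 30 mg points.
2. SAP section 7.3 sets its minimum number of evaluable values per dose for tables that are themselves laid out by cohort. In this SAP, dose can therefore stand for the dose group of a cohort.
3. The Cohort 3 note is needed because that single cohort held two dosing patterns, so a by-cohort split would not part them. The two routes at 30 mg are in Cohorts 2 and 7, and a by-cohort split parts them with no extra rule.
4. Protocol Table 1 gives 30 mg IV and 30 mg SC their own columns, each with its own dose-normalised geometric mean. Protocol section 1.2.5.2 confines its linearity statement to the 10–1000 mg IV doses and uses the two 30 mg groups only to estimate F. SAP Table 1 keeps CL for IV apart from CL/F for SC.

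**The case for a change.** The case for an edit is fair. The plot sentence says dose where neighbouring items on concentrations say cohort and dose, so the difference might be deliberate. The SAP names route for clearance, volume and immunogenicity but not here. The footnote is inaccurate: six Part 1 cohorts were dosed (1, 2, 3, 4, 5 and 7). Plotted individual values are only a partial safeguard, because the SAP asks for different symbols for means and individuals, not for routes. Taking geometric mean × exp(±2s), with s = √ln(1 + CV²) and log-normal values, the 30 mg Cmax(dn) ranges are 0.275–0.608 (IV) and 0.036–0.188 (SC), which separate by eye. The AUCinf(dn) ranges are 281–843 and 139–584, which do not.

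Two things stand: the sentence has no route term, and the footnote is loose. It does not follow that the plan directs pooling. That reading takes one phrase apart from the by-cohort summaries around it and from the sponsor's own reporting. Nor would a mixed mean go unnoticed, since the by-cohort tables of dose-normalised AUCinf and Cmax would sit beside it and disagree.

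**Conclusion.** No change is needed. This is a gap in wording that analysts fill sensibly. The by-cohort reading is the better supported one, and under it nothing is misplaced. Under the other reading the damage is one plotted symbol per figure: large for Cmax (55% below the 30 mg IV mean), modest for AUCinf (23% below it, and 3.6% below the lowest IV mean). SAP sections 4.1 and 4.2 state that no hypothesis is tested and no decision rule is used, so nothing formal depends on the plot. Dose proportionality is not a listed objective; the secondary PK objective is to characterise the profile, which the by-cohort tables serve. The primary safety objective is untouched.

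The sizes rest on preliminary Table 1 data with six subjects per route, and final values may differ. The conclusion does not rest on them, because it depends on how the SAP defines its geometric means and on the two routes being in separate cohorts.
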